16.5 Data & Safety Monitoring

16.51 This study will be monitored by the Mayo Data Safety Monitoring Board (DSMB) every 6 months. Toxicity, efficacy and administrative information for this trial will be reviewed by the study team routinely.

16.52 Adverse Event Stopping Rules

The stopping rules specified below are based on the knowledge available at study development. We note that the Adverse Event Stopping Rule may be adjusted in the event of either (1) the study reopening to accrual or (2) at any time during the conduct of the trial and in consideration of newly acquired information regarding the adverse event profile of the treatment(s) under investigation. The study team may choose to suspend accrual because of unexpected adverse event profiles that have not crossed the specified rule below.

16.521 Phase I/Ib Adverse Event Stopping Rule

During the first 2 cycles, 4 of the initial 10 treated patients or 40% or more of all patients (i.e., when accrual is greater than 10 patients) have experienced a Grade 4+ adverse event at least possibly related to study treatment, per NCI Common Terminology Criteria for Adverse Events v.5.0, excluding the following:

- Grade 4 neutrophil count decreased lasting ≤ 7 days
- Grade 4 white blood cell decreased lasting ≤ 7 days
- Grade 4 platelet count decreased lasting ≤ 7 days
- Grade 4 diarrhea responding to optimal support

16.522 Phase II Adverse Event Stopping Rules

Accrual will be temporarily suspended to this study if at any time we observe events considered at least possibly related to study treatment (i.e. an adverse event with attribute specified as “possible”, “probable”, or “definite”) that satisfy either of the following:

- If 1 or more patients out of the first 6 patients (either HRD encompassing BRCA1, BRCA2, PALB2 or other HRD) experience grade 5 events (death) deemed at least possible (possible, probably, or definite) related to MFR, the accrual to the study will be suspended to allow for investigation. After consideration by the study team (study chair, statistician) and consultation with the sponsor, a decision will be made as to whether accrual can be resumed.
- If 6 or more patients among the first 20 patients (either HRD encompassing BRCA1, BRCA2, PALB2 or other HRD) enrolled

or 30% of the patients thereafter develop a grade4+ non-hematologic toxicities at least possible (possibly, probably or definitely) related to treatment, enrollment will be suspended so that the adverse event data can be examined and a trial recommendation will be formulated and presented to Mayo DSMB.

- We note that we will review grade 4 and 5 adverse events deemed “unrelated” or “unlikely to be related”, to verify their attribution and to monitor the emergence of a previously unrecognized treatment-related adverse event.

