The recommended dose determined by phase I dose escalation is dose level 2-A (DL2-A in section 7.11)

Agent	Dose	Route	Day
nal-IRI	50 mg/m ² (Recommended Dose Determined by Phase I Dose Escalation)	Intravenous over 90 minutes	Days 1 and 15
5-FU	2400 mg/m ²	Intravenous over 46 hours	Day 1 and 15
Rucaparib	600 mg (Recommended Dose Determined by Phase I Dose Escalation)	Oral	Twice daily on Days 4-13 and days 18-27 (Recommended schedule determined by phase I dose escalation)

7.13 Phase II (Phase II study at recommended dose level determined by the Phase I portion)

Agent	Dose	Route	Day
nal-IRI	Recommended Dose Determined by Phase I Dose Escalation	Intravenous over 90 minutes	Days 1 and 15
5-FU	2400 mg/m ²	Intravenous over 46 hours	Days 1 and 15
Rucaparib	Recommended Dose Determined by Phase I Dose Escalation	Oral	Twice daily on days as determined by Phase I administration schedule

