	CTCAE grade 3 edema lasting fewer than 5 days
	Grade 3 laboratory abnormalities that are responsive to oral supplementation or deemed by the investigator to be not clinically significant
CTCAE version 4.03 will be used for all grading. Optimal therapy for vomiting or diarrhea will be based in institutional guidelines, with consideration of the prohibited medications listed in this protocol.	

7.5 Phase II - The phase II study in pancreatic cancer will depend on the successful completion of the phase I trial, determination of the recommended dose level and discussion between PI and co-sponsors of the study.

7.51 Following the accrual of the first 6 patients into the phase II portion, we will assess for any unexpected serious toxicities (without halting accrual). If >1 of the first 6 patients experience grade 5 toxicity at least possibly (possible, probable, definite) related to treatment, we will halt accrual and discuss with the sponsors alternative dose levels including the possibility to de-escalate to one dose level. After reinitiating accrual, the patients who were included in the prior dose level cannot be considered for the final analysis and will have to be replaced.

7.52 In the Phase II portion of this study, all patients' tissue samples will be screened for HRD and BRCA-like signature, and only those patients with defects will be selected for the treatment study.

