irinotecan, primarily based on a qualitative comparison of adverse reactions, as reported in the Camptosar US Product label for irinotecan, and as summarized in this document and reflected in the US Product Label for irinotecan liposome injection. The comparison is qualitative, since both irinotecan and irinotecan liposome injection have been used in different doses and schedules as monotherapy and combination therapy with other chemotherapeutic agents; making quantitative comparisons are difficult. The most common adverse reactions of irinotecan and irinotecan liposome injection are similar and are mainly gastrointestinal events and myelosuppression.

In single agent irinotecan therapy clinical studies, the most common adverse reactions ($\geq 30\%$) observed are: nausea, vomiting, abdominal pain, diarrhea, constipation, anorexia, neutropenia, leukopenia (including lymphocytopenia), anemia, asthenia, fever, body weight decreasing, and alopecia.

Comparatively, irinotecan liposome injection, when used in combination with 5-fluorouracil and leucovorin, the most common adverse reactions ($\geq 20\%$) observed in clinical trials considered were: diarrhea, fatigue/asthenia, nausea, vomiting, decreased appetite, stomatitis, and pyrexia. The most common laboratory abnormalities ($\geq 10\%$ Grade 3 or 4) were lymphopenia and neutropenia (ONIVYDE USPI).

Certain known adverse reactions of irinotecan have not been observed with irinotecan liposome injection to date. This could be due to the limited cumulative patient exposure to date of irinotecan liposome injection, or the use of appropriate premedication and early recognition and treatment of expected adverse events. The adverse reactions observed with irinotecan and not yet observed with irinotecan liposome injection include anaphylaxis or anaphylactoid reaction, interstitial lung disease-like pulmonary toxicity and acute pancreatitis. There is insufficient evidence to know whether these known adverse reactions of irinotecan will also be associated with irinotecan liposome injection.

15.28 **Drug procurement:**

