Ipsen will provide the commercial formula of irinotecan liposome free of charge to Clinical Research Services, a division of Rx Crossroads by McKesson for investigational use in this study. The product will be labeled, "For Investigational Use." Each participating ACCRU treating location will order the drug from Clinical Research Services, a division of Rx Crossroads by McKesson. It will take 1-2 business days to receive the nal-IRI.

Fax or email the Drug Order Request Form (found on the ACCRU web site) to:

Each participating ACCRU treating location will be responsible for monitoring the supply of nal-IRI and will use the appropriate Drug Order Request Form to order additional supplies as needed.

Outdated or remaining drug is to be destroyed on-site as per procedures in place at each institution.

15.29 Nursing Guidelines:

- 15.291 If possible, check for any history of hypersensitivity reaction to any previous drug formulated with polysorbate 80.
- 15.292 Cholinergic symptoms of lacrimation, nasal congestion, diaphoresis, flushing, ABD cramping, and diarrhea can occur at the beginning, during, or immediately after the irinotecan liposome infusion. It is suggested that the patient remain in the treatment area for a minimum of one hour following the completion of the **very first** irinotecan liposome infusion. If diarrhea occurs within one hour of infusion, refer to Section 9.2 or 15.16 for management.
- 15.293 Patient education is extremely important. Impress on the patient the importance of compliance with treatment of diarrhea management (see Section 9.4). Stress the need for prompt recognition and early intervention. Motivate the patient to report any complications immediately. The cholera-like syndrome can be unresponsive to conventional antidiarrheals and can result in severe dehydration.
- 15.294 Ondansetron and diphenhydramine should provide good relief from the nausea/vomiting/cramping. Avoid prochlorperazine on the day of treatment due to its association with akathisia (motor restlessness). Prochlorperazine may be taken between treatments.
- 15.295 Advise avoidance of excess caffeine, a GI stimulant. Avoid magnesium-based antacids such as Mylanta, Maalox, Rolaids, MOM, Mag-Ox 400, and Tylenol with antacid.
- 15.296 The pulmonary toxicity seen is usually manifested by dyspnea beginning 42-175 days after treatment and occurs at a cumulative dose ranging from 400-1000 mg/m (median 750). Instruct patient to report any cough or SOB.

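### Phase I/Ib has no accrual pause for a treatment-related death: early deaths count only as grade 4+ events, deaths from cycle 3 count for nothing, and any pause for them is discretionary

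*Combined protocol and SAP*

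**What the plan says.** Section 16.521 sets the Phase I/Ib limit as "During the first 2 cycles, 4 of the initial 10 treated patients or 40% or more of all patients" with a grade 4 or higher event at least possibly related to treatment. Four listed kinds of grade 4 event are excluded. Grade 5 falls within grade 4 or higher and has no line of its own. For anything short of the limit, 16.52 says "The study team may choose to suspend accrual because of unexpected adverse event profiles that have not crossed the specified rule below".

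Phase II is handled differently. Section 16.522 opens with "Accrual will be temporarily suspended to this study if at any time we observe events considered at least possibly related to study treatment" and its first condition reads "If 1 or more patients out of the first 6 patients (either HRD encompassing BRCA1, BRCA2, PALB2 or other HRD) experience grade 5 events". Section 7.51 covers the same first 6 patients with another threshold: "If >1 of the first 6 patients experience grade 5 toxicity at least possibly (possible, probable, definite) related to treatment, we will halt accrual".

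Other relevant provisions:
- A cycle is 28 days (7.1). Treatment may continue until progression or 3 years (13.1).
- DLTs are assessed in cycle 1 and drive dose escalation only (7.42, 16.22).
- Escalation has finished: "The recommended dose determined by phase I dose escalation is dose level 2-A" (7.12).
- Phase Ib plans 40 patients (16.12) at 3-4 per month (16.13). Further tolerability is part of its primary aim (2.21).
- Deaths within 30 days of the last dose, and later deaths judged related, are reported within 24 hours (10.312). The DSMB reviews every 6 months and the study team routinely (16.51).

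**The concern.** A treatment-related death is the most serious safety signal a trial can produce. Sponsors commonly require enrolment to stop while such a death is examined, and this sponsor does so at the start of Phase II. In Phase I/Ib no equivalent requirement exists. A death inside the first two cycles carries the same weight as a grade 4 laboratory event outside the exclusion list, and a later death carries none.

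At stake is whether further patients are enrolled on the regimen before someone has had to decide that this is acceptable. Phase Ib is the last step before untreated patients receive the combination, so it is an odd place for the weaker protection. The plan states no operating characteristics for 16.521, so it offers no figure to reproduce.

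**Working it through.** **1. Reach of the window.** Two cycles are 2 × 28 = 56 days. The Phase Ib endpoint of disease control for at least 24 weeks spans 24 × 7 / 28 = 6 cycles. Three years is about 3 × 365 / 28 ≈ 39 cycles. Events in cycle 3 or later add 0 to the count, however many there are.

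**2. Patients needed to cross the limit.** The limit is 4 in the first 10, then the smallest whole number that is at least 0.4n.

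| Patients | Needed to cross | Largest number not crossing |
|---|---|---|
| 10 | 4 | 3 |
| 20 | 8 | 7 |
| 30 | 12 | 11 |
| 40 | 16 | 15 (37.5%) |
| 49 | 20 | 19 |
| 58 | 24 | 23 |

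The last two rows apply if escalation and expansion are counted together (49 to 58 patients, 16.12).

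**3. How the count responds to deaths.** Suppose, purely for illustration, a 10% risk of related death within two cycles and no other counted events. The first-10 part of the rule is crossed with probability P(X ≥ 4), X ~ Binomial(10, 0.10), which is 0.0128, or 1.3%. The chance of at least one such death among those 10 is 1 − 0.90^10 = 0.651. The limit works as a general toxicity boundary; it does not react to a single death.

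**4. Whether another rule fills the gap.**
- *DLT rule.* A related non-hematologic event of grade 3 or higher is in general a DLT, so a related cycle 1 death in escalation would ordinarily count. Two DLTs in 6 patients end accrual to that cohort, while one in 3 leads to up to 3 more patients at the same level (16.224). The rule stops at day 28, and no DLT-based accrual rule is stated for Phase Ib.
- *Reporting and review.* These make a death known and state no accrual action. At 3-4 patients per month, 6 × 3 = 18 to 6 × 4 = 24 of the 40 Phase Ib patients could enrol between two DSMB reviews.
- *Section 16.52.* Suspension below the limit, and adjustment of the rule itself, are both permitted and not required.
- *Phase II triggers.* 16.522 and 7.51 do not apply to Phase I/Ib.

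**5. Cost of a single-death pause.** Let q be the related-death risk per patient, assumed because the plan gives none. The chance of at least one related death in 40 patients is 1 − (1 − q)^40.

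| Assumed q | Expected deaths (40q) | Chance of at least one |
|---|---|---|
| 0.5% | 0.2 | 0.182 |
| 1% | 0.4 | 0.331 |
| 2% | 0.8 | 0.554 |

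These are upper limits on the chance of a pause. A death after the 40th patient has enrolled cannot pause accrual, and Phase Ib is expected to take up to 20 months (16.13).

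**The case against.** The strongest reply is that late deaths do not go unnoticed. All serious adverse events in Phase I/Ib are reported on an expedited basis (10.311). Pneumonitis, myelodysplastic syndrome and secondary leukemia are events of special interest with 24-hour reporting (10.4), and related serious events more than 30 days after the last dose are still expedited. An attentive team would probably pause without being told to. That stands, and it limits the point to a required pause versus a discretionary one.

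It is also fair that the Phase II comparator is imperfect. Sections 7.51 and 16.522 disagree (more than 1 death against 1 or more), and neither has a death-specific trigger after patient 6.

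A reader might infer three stronger things that the documents do not support:

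- *That the two-cycle window is itself a fault.* Section 8.0 treats the first two cycles as the period for establishing individual tolerance, so this is a reasonable window for a 40% toxicity count.
- *That three deaths in the first 10 patients would pass without consequence.* At least 49 − 40 = 9 patients belong to dose escalation. If the first 10 are counted across Phase I/Ib, most fall under the 3+3 rules, where a related cycle 1 death would ordinarily be a DLT.
- *That a known delayed lung toxicity falls beyond the window.* Section 15.296 says "The pulmonary toxicity seen is usually manifested by dyspnea beginning 42-175 days after treatment and occurs at a cumulative dose ranging from 400-1000 mg/m". Onset from day 42 lies partly inside the 56 days. Section 15.27 says "The adverse reactions observed with irinotecan and not yet observed with irinotecan liposome injection include anaphylaxis or anaphylactoid reaction, interstitial lung disease-like pulmonary toxicity". Applying that cumulative-dose range to the liposomal product assumes a dose equivalence that the documents do not give.

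**Conclusion.** The point holds as a gap in Phase I/Ib, chiefly in Phase Ib. Section 16.521 has no death-specific trigger. Related deaths in cycles 1-2 are pooled with grade 4 events against 4 of 10 or 40%, and related deaths from cycle 3 are not counted. No other provision requires a pause for them. This follows from the text and needs no assumption about event rates, apart from reading the first 2 cycles as each patient's own.

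The documents do not show how often such deaths would occur or what share would be late, so no estimate of patients harmed is offered. The pause probabilities rest on assumed risks and independence between patients. This is an inexpensive improvement worth considering; it does not make the trial unsafe as designed.

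**What to change.** Add to 16.521: *Accrual will be temporarily suspended for review if any patient has a grade 5 event at least possibly related to study treatment, in any cycle.* Let resumption be decided as in 16.522, by the study team in consultation with the sponsor. Keep the 2-cycle count of 4 of 10 or 40% unchanged. State the action explicitly, because 16.521 does not say what happens when its own limit is reached. In the same amendment, reconcile 7.51 with 16.522.

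The cost is one sentence and an occasional temporary pause, with the probabilities given above as upper limits. The deaths are already reported within 24 hours, so no new data collection is needed. The sponsor should know that this is broader than Phase II, where the single-death rule covers only the first 6 patients.

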16.12 Sample Size

The phase I portion of this study is expected to require a minimum of 49 patients and a maximum of 58 patients including 40 patients who will be accrued into the expanded phase Ib cohort (see below).

The phase Ib portion of this trial consists of 2 expansion cohorts of patients adenocarcinoma who have received no more than 1 line of prior therapy in the metastatic setting. The objective of the phase Ib study is exploratory and hypothesis generating in nature. The phase 1b analysis is not powered; thus, no sample sizes were derived. We plan to enroll 40 patients to the Phase Ib, including 28 patients with either unknown mutation status or non-HRD (known wildtype for BRCA1, BRCA2, and PALB2 genes) and 12 patients with known HR deficiency (known mutation in either BRCA1, BRCA2, or PALB2 genes) with the intent of establishing the efficacy of rucaparib in combination with nal-IRI. In addition to 12 patients with known HR deficiency due to mutations in BRCA1, BRCA2, or PALB2, we expect that 7 of 28 Unknown/Non-HRD cohort patients will have HR deficiency since 25% of PDAC patients have defects in DNA repair.

The phase II portion of this study is expected to require a minimum of 11 and a maximum of 21 untreated pancreatic patients with HRD encompassing BRCA1, BRCA2, or PALB2 deleterious mutations (germline and somatic). An additional 3 patients with untreated pancreatic cancer and with BRCA1, BRCA2 or PALB2 deleterious mutation will be accrued to account for ineligibility, cancellation, major treatment violation, or other reasons. We anticipate accruing patients with

other HRD (other than BRCA1, BRCA2, or PALB2) during the phase II portion of the trial for exploratory analysis. Therefore, the phase II portion is expected to screen 200 patients and accrue 24 patients with HRD encompassing BRCA1, BRCA2 and PALB2 patients and another 28 patients with other HRD with an overall sample size will be a maximum of 52 patients.

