- 16.228 DL2-A (formerly known as DL1-A) was added as an intermediate dose level between DL 1 and DL2-B (formerly known as DL2) (Amendment 3). Following the approval of Amendment 3, enrollment will re-open to DL2-A. If DLTs are seen in less than 2 out of 6 patients treated at DL2-A then DL2-A will be considered the MTD. If DLTs are observed in at

least 2 patients treated at DL2-A then enrollment will resume at the next lowest DL until MTD is met.

- 16.23 Analysis plans: All the relevant results pertaining to toxicity, MTD, laboratory correlates will be examined in an exploratory and hypothesis-generating fashion.
- 16.231 Adverse events profile: The number and severity of all adverse events (overall, by dose-level, and by tumor group) will be tabulated and summarized in this patient population. The grade 3+ adverse events will also be described and summarized in a similar fashion. This will provide an indication of the level of tolerance for this treatment combination in this patient group
- 16.232 Toxicity Profile: The term toxicity is defined as adverse events that are classified as either possibly, probably, or definitely related to study treatment. Non-hematologic toxicities will be evaluated via the ordinal CTC standard toxicity grading. Hematologic toxicity measures of thrombocytopenia, neutropenia, and leukopenia will be assessed using continuous variables as the outcome measures (primarily nadir) as well as categorization via CTC standard toxicity grading. Overall toxicity incidence as well as toxicity profiles by dose level, patient and tumor site will be explored and summarized.
- 16.233 Response: Objective responses, as defined per RECIST 1.1, will be summarized by simple descriptive summary statistics delineating complete and partial responses as well as stable and progressive disease.

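### The Phase I/Ib adverse event boundary counts escalation patients from other dose levels, so it is a weak and late check on toxicity at the recommended dose in Phase Ib

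*Combined protocol and SAP*

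**What the plan says.** Section 16.521 is headed as a rule for Phase I/Ib. Over the first two cycles it counts those who "have experienced a Grade 4+ adverse event at least possibly related to study treatment"; four kinds of event are excluded. The threshold is set as follows: "4 of the initial 10 treated patients or 40% or more of all patients (i.e., when accrual is greater than 10 patients". Nothing in the section separates the phases or the dose levels.

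Section 16.12 gives the combined size as "a minimum of 49 patients and a maximum of 58 patients including 40 patients who will be accrued into the expanded phase Ib cohort". Section 7.12 fixes the Phase Ib dose: "The recommended dose determined by phase I dose escalation is dose level 2-A". Escalation was not confined to that level: Section 16.228 says that DL2-A "was added as an intermediate dose level between DL 1 and DL2-B". Section 2.21 makes further tolerability of the recommended dose part of the Phase Ib primary aim.

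Section 16.521 states a condition and its exclusions but no consequence. Section 16.522, for Phase II, opens with one: "Accrual will be temporarily suspended to this study if at any time we observe events considered at least possibly related to study treatment".

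**The concern.** A boundary meant to protect patients at one dose should be driven by patients at that dose. Here the early look belongs almost entirely to escalation, and the later cumulative look averages Phase Ib with patients treated below and above DL2-A. If the escalation Grade 4+ rate was under 40%, every escalation patient carried forward pulls the pooled proportion down. The Phase Ib rate then has to run above 40% before the rule is met.

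At stake is the only numeric stopping boundary for the 40 Phase Ib patients. The DLT assessment in Section 7.42 covers 28 days in escalation only, whereas 16.521 covers two cycles.

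**Working it through.** **The plan's own figures.** Section 16.21 says that 6 patients show a toxicity of 25% incidence with probability of at least 82%: 1 − 0.75^6 = 0.822, which agrees. The escalation size follows from Section 16.12: 49 − 40 = 9 and 58 − 40 = 18. No operating characteristics are given for 16.521, so there is nothing further to reproduce.

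**Step 1: the 4-of-10 look.** With 9 escalation patients, one of the first 10 places is left for Phase Ib. With 10 or more, none is left.

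**Step 2: events needed at full accrual.** With m escalation patients and x events among them, the pooled rule at Phase Ib patient 40 needs the smallest whole number of at least 0.4(m + 40), minus x.
- m = 9: 0.4 × 49 = 19.6, so 20 − x. For x = 0 to 3 this is 20 down to 17.
- m = 18: 0.4 × 58 = 23.2, so 24 − x. For x = 0 to 3 this is 24 down to 21.
- Phase Ib alone: 0.4 × 40 = 16.

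The pooled rule thus needs 17 to 24 events in 40 (43% to 60%), against 16 in 40 (40%).

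**Step 3: probability that the rule is met.** This is an exact binomial recursion with a look after every patient. The rule is met at 4 or more events while n ≤ 10, and at k/n ≥ 0.40 once n > 10. Assumptions not in the documents: an escalation event rate of 10% to 20%, outcomes known at once, and no crossing during escalation. The last column starts from 6 DL2-A escalation patients with 1 event (also assumed) and adds the 40 Phase Ib patients.

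| True Phase Ib rate | Pooled, 18 escalation patients | Pooled, 9 escalation patients | Phase Ib alone | DL2-A patients plus Phase Ib |
|---|---|---|---|---|
| 20% | 0–1% | 2–7% | 15% | 5% |
| 30% | 1–5% | 10–20% | 47% | 24% |
| 40% | 10–23% | 38–51% | 83% | 62% |
| 50% | 42–61% | 78–85% | 98% | 92% |
| 60% | 82–91% | 97–98% | 99.9% | 99.5% |

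Within each pooled range, the lower figure is for a 10% escalation rate and the upper for 20%. Extending the assumption down to 5% lowers the bottom of the overall pooled range to 5% at a true 40%, 31% at 50% and 75% at 60%.

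**Step 4: timing.** Take 2 events in 15 escalation patients and a true Phase Ib rate of 50%. By Phase Ib patient 20 the pooled rule has been met in 28% of trials, against 93% for Phase Ib alone. The expected number of Phase Ib patients treated is 29.6 against 9.6.

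**Step 5: when the dilution fades.** With 5 events in 15 escalation patients, the pooled rule is met in 95% of trials at a true 50%. With 6 in 18 it is 93%.

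**The case against.** The strongest reply is that the size of the effect rests on escalation rates that the documents do not give. Escalation included DL2-B, above the recommended dose, and up to 6 patients at DL2-A itself, so a low escalation rate cannot be taken for granted. Step 5 shows that most of the gap closes at a true 50% if escalation was toxic. This stands, and it is why the result is a range under stated assumptions.

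Second, the 83% for Phase Ib alone is not purely the absence of dilution. Restarting the rule adds fresh early looks; a single look for 16 or more of 40 at a true 40% gives 56%. The same early looks produce suspensions in 47% of trials at a true 30%, which is below the plan's own limit. This also stands. It argues against counting Phase Ib alone, which would discard the DL2-A escalation patients treated at the same dose.

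Third, a reader might infer that excess toxicity in Phase Ib would go unnoticed. The documents do not support that. Section 16.51 provides DSMB review every 6 months and routine study team review. Section 10.311 puts all SAEs in Phases I and Ib under expedited reporting. Section 16.52 lets the team suspend accrual below the boundary. These do not replace a working boundary: at 3–4 patients per month (Section 16.13), 18 to 24 Phase Ib patients can enter between DSMB reviews, and suspension below the boundary is optional.

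Fourth, a reader might infer that nothing happens when 16.521 is met, or that the missing action causes the dilution. Neither follows. The heading and preamble of 16.52 imply suspension of accrual, and the missing consequence is a separate drafting gap.

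**Conclusion.** On its plain wording, 16.521 pools patients across phases and dose levels. That weakens and delays the formal boundary for Phase Ib whenever the escalation Grade 4+ rate is below 40%. With 9 to 18 escalation patients, an assumed escalation rate of 10–20% and no crossing in escalation, the loss is large at true Phase Ib rates of 40% (10–51% against 83%) and 50% (42–85% against 98%). At 60% it is mainly a matter of delay (82–98% against 99.9%).

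It would be too strong to say that the rule usually misses excess toxicity. That depends on unknown escalation rates, is not so at a true 60%, and concerns the formal boundary only. The direction is firm and the size is conditional. The rule should be changed, because tolerability at the recommended dose is part of the Phase Ib primary aim.

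**What to change.** In 16.521, apply the existing thresholds (4 of the first 10, then 40%) separately to patients treated at the recommended dose, meaning the DL2-A escalation patients plus Phase Ib. If there were 6 such escalation patients, the 4-of-10 look would fall at the fourth Phase Ib patient.

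State the operating characteristics with the revision, using the actual DL2-A counts, because the result depends on them. With 1 event in 6, the rule is met in 62% of trials at a true 40% and 92% at 50%. With no events in 6, these fall to 42% and 83%.

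The cost is a few sentences and more temporary suspensions when toxicity is acceptable: 5% of trials at a true 20% and 24% at 30% (with 1 event in 6), against about 0–7% and 1–20% with pooling. Counting Phase Ib alone would cost 15% and 47%.

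As a separate minor clarification, write into 16.521 the action that 16.522 already uses: accrual temporarily suspended for review.

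### In Phase II, a related death from patient 7 on has no trigger of its own, and a related hematologic death then meets neither mandatory suspension rule

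*Combined protocol and SAP*

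**What the plan says.** Section 16.522 suspends Phase II accrual for related events "that satisfy either of the following". Throughout, related means attributed as possible, probable or definite.

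- **First bullet, deaths:** "If 1 or more patients out of the first 6 patients" have a related grade 5 event. The study team considers the matter and consults the sponsor, and "a decision will be made as to whether accrual can be resumed". The DSMB is not named.
- **Second bullet, toxicity:** "If 6 or more patients among the first 20 patients", or "30% of the patients thereafter develop a grade4+ non-hematologic toxicities". Enrollment is suspended and a recommendation goes to the DSMB.

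Other provisions that bear on this:

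- The 16.52 preamble lets the study team suspend accrual below the thresholds, for adverse event profiles that are unexpected, and lets the rules be adjusted during the trial.
- Section 16.51: "This study will be monitored by the Mayo Data Safety Monitoring Board (DSMB) every 6 months".
- Section 10.312 requires 24-hour reporting of any death within 30 days of the last dose, and of later deaths if related.
- Section 16.521 (Phase I/Ib) counts related grade 4+ events of any type. Each of its exclusions is limited to grade 4.
- Section 16.12 sets a Phase II maximum of 52 patients.

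**The concern.** A related death in patient 6 suspends accrual. The same death in patient 7 does not, and no reason is given. If it is non-hematologic, it adds one to a count that needs 6 in the first 20 patients or 30% later, as a survived grade 4 event would. If it is hematologic, it adds nothing.

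The second case is foreseeable. Section 15.299a warns that grade 4 diarrhea together with grade 4 neutropenia can lead to sepsis and death, and 10.521 lists febrile neutropenia under blood and lymphatic disorders. Section 16.522 does not define non-hematologic, so it is open whether a neutropenic-sepsis death counts.

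DSMB involvement also runs the wrong way round: the toxicity count leads to the DSMB, while a death among the first 6 is settled by the study team with the sponsor. What is at stake is timely independent review of the most serious safety outcome.

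**Working it through.** **Inputs from the documents.** Maximum Phase II size 52 (16.12). Death trigger: 1 or more of the first 6. Toxicity trigger: 6 of 20, then 30% (16.522). Accrual 12 to 24 months (16.13). DSMB every 6 months (16.51).

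**Assumptions.** The documents give no related-death rate (q), no background rate of survived grade 4 non-hematologic toxicity (g), and no operating characteristics for the safety rules. Ranges are shown. Background toxicity is taken as independent of death, each patient counts once, the rules are checked after every patient, and the 30% is read as a proportion of all patients so far.

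**Size and coverage.** 21 + 3 + 28 = 52, which reproduces the plan's figure. Outside the death trigger: 52 − 6 = 46, and 46/52 = 88%. The cut is by patient, not date: a late death in one of the first 6 still meets the first bullet.

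**Height of the second trigger.** 6/20 = 30%, so its two parts agree. After patient 20 it needs the next whole number at or above 0.3n: 7 at n = 21, 9 at 30, 12 at 40 and 16 at 52 (0.3 × 52 = 15.6). With no other grade 4+ non-hematologic event, up to 5 related non-hematologic deaths among patients 7 to 20, and up to 15 by patient 52, can occur without mandatory suspension. Related hematologic deaths in patients 7 to 52 have no limit.

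**Chance that no rule fires through 52 patients.** This is P(no death in the first 6) = (1 − q)^6, times P(second trigger never crossed, given that), the latter by exact recursion over patients. At q = 5%, 0.95^6 = 0.735. At q = 10%, 0.90^6 = 0.531.

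| q | Type of death | g = 0% | g = 10% | g = 20% |
|---|---|---|---|---|
| 5% | all non-hematologic | 73.5% | 70% | 42% |
| 5% | all hematologic | 73.5% | 72.5% | 54% |
| 10% | all non-hematologic | 53% | 46% | 21% |

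For hematologic deaths only background events can cross the second trigger, with probability 0.0131 at g = 10% and 0.2644 at g = 20%: 0.735 × (1 − 0.0131) = 0.725 and 0.735 × (1 − 0.2644) = 0.541.

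**Deaths in the uncovered patients.** Binomial with n = 46:

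| q | P(first bullet fires) = 1 − (1 − q)^6 | P(2 or more deaths in patients 7–52) |
|---|---|---|
| 1% | 5.9% | 7.8% |
| 2% | 11.4% | 23.5% |
| 5% | 26.5% | 67.7% |
| 10% | 46.9% | 95.2% |

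**Exposure between DSMB reviews.** If all 52 accrue within the stated 12 to 24 months, 6 × 52/24 = 13 to 6 × 52/12 = 26 patients enter between reviews. Section 16.13 gives that period when discussing the BRCA1/2 and PALB2 patients, so applying it to all 52 is an assumption.

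**The case against.** **The deaths are not invisible.** A reader might infer that related hematologic deaths count nowhere. The documents do not support that. Such deaths are reported within 24 hours (10.312), forwarded to the drug suppliers (10.4), tabulated (16.432c), and covered by routine study-team review and six-monthly DSMB monitoring (16.51). The study team may also suspend accrual. This stands, and it limits the point to mandatory rules. None of these steps compels a suspension or a prompt DSMB review, and the discretionary clause speaks of unexpected profiles.

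**The size is sensitive to assumptions.** A reader might take 53% as the chance that no rule fires at a 10% death rate. It needs no survived grade 4 non-hematologic events at all, in a regimen whose common toxicities are gastrointestinal; it falls to 46% and 21% at background rates of 10% and 20%. If the 30% applies only to patients enrolled after the 20th and is checked patient by patient, 53% becomes 37%. That reading lets one event among the first three such patients trigger suspension (1/3 = 33%), so the cumulative reading is more natural, but the text does not settle it.

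**High death rates should already have shown.** Section 16.228 plans 6 patients at DL2-A and Phase Ib plans 40 more at that level. With 46 patients, the chance of seeing no related death is 0.90^46 = 0.8% at a 10% rate and 0.95^46 = 9% at 5%. This stands: rates of 10% or more are unlikely to reach Phase II unnoticed, and at 1% to 2% the chance of two or more deaths in patients 7 to 52 is 8% to 24%.

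**The limit to 6 patients is deliberate.** Section 16.4 describes a safety run-in. That explains an early death rule. It does not explain leaving hematologic deaths out of the later count, which the Phase I/Ib rule does not do.

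**Conclusion.** The gap is real and follows from the text alone: from patient 7 on, up to 46 of 52 patients, a related death has no trigger of its own, and a related hematologic death meets neither mandatory rule. At an assumed 5% related-death rate, the chance that no rule fires ranges from 42% to about 74% across the background rates and types of death shown, with the 30% read cumulatively. The percentages are illustrations; the absence of a mandatory response does not depend on them.

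A reader might also infer that every related death ought to suspend accrual automatically. The documents neither require nor contradict this. It trades interruptions against caution and is for the sponsor and DSMB to weigh.

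A separate contradiction concerns the first 6 patients: 7.51 halts accrual at more than 1 related grade 5 event, 16.522 at 1 or more. The two must be reconciled.

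**What to change.** 1. Reword the second bullet of 16.522 so that it counts related grade 4+ non-hematologic toxicities and related grade 5 events of any organ class. State whether the 30% is cumulative.
2. Require every related grade 5 event in any Phase II patient, including the first 6, to go promptly to the DSMB, which advises whether accrual should pause.
3. Reconcile the thresholds in 7.51 and 16.522.

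Item 1 alone does little: it moves the hematologic row of the table to the non-hematologic one (at 5%, from 73.5%, 72.5% and 54% to 73.5%, 70% and 42%). Item 2 does most of the work, because review then no longer depends on a count. Automatic suspension for each single related death remains an option.

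The cost is amendment wording and one ad hoc DSMB review per related death. Over patients 7 to 52 the expected number is 46q: about 0.9, 1.4, 2.3 and 4.6 at related-death rates of 2%, 3%, 5% and 10%. The first 6 patients add 6q, or 0.1 to 0.6 over the same range.
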